Before administration of propofol, remifentanil infusion at a rate of 0.05 µg/kg/min was started. Five minutes after start of remifentanil infusion, an attending anesthesiologist administered propofol (1 mg/kg) mixed with lidocaine (1 mg/kg) over 1 minute followed by continuous infusion of propofol on the basis of clinical signs of arousability, movement, blood pressure, heart rate and respiratory rate in a spontaneous breathing child. Two independent investigators assessed the level of sedation using the clinical sedation scale such as UMSS and the modified Observer's Assessment of Alertness/Sedation (MOAAS) every minute during induction and maintenance of sedation (Table 1). MOAAS includes only the responsiveness component of the original OAA/S (5). These two observers performing the clinical sedation score assessments were blinded to the BIS monitor throughout study period. Another third investigator recorded the BIS and EMG values, oxygen saturation, respiratory rate, blood pressure and heart rate immediately before each assessment of clinical sedation score. The BIS and EMG values with a signal quality index (SQI) ≥ 50 were accepted for analysis. Deep sedation was defined based on clinical sedation scale categories: a UMSS score of 3-4 or a MOAAS score of 0-1.

Statistical analysis plan

Document Date: April 30, 2017

Uploaded: June 10, 2018

The sample size was calculated with α error of 0.05 and a power of 80% to determine the validity of BIS values to detect deep sedation in children with cerebral palsy. A minimum 19 participants was required to detect a correlation coefficient of 0.6 for repeated measures. We enrolled 22 patients, taking into consideration of 15% drop-out rate.

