Statistical analysis was performed with SPSS version 22.0 (SPSS Inc, Chicago, IL, USA) for Windows. Continuous variables were presented as mean \pm standard deviation for normal distributed data or the median and interquartile range for non-normal distributed data after the Kolmogorov-Smirnov test with Lilliefors correction. Categorical variables were presented as number of patients (%). The BIS values at each UMSS and MOAAS score were compared using one-way ANOVA followed multiple pairwise comparisons with Bonferroni correction. BIS values were categorized into ranges of <50, 50-59, 60-69, 70-79, 80-89 and 90 or higher. The Kappa was calculated to determine the agreement between the BIS value categories and clinical sedation score between 2 independent observers. A kappa ≥ 0.7 was considered good agreement. The correlation between the paired BIS value categories and clinical sedation scores was determined by Spearman rank correlation test. Receiver operating characteristic (ROC) curve analysis was performed to determine the sensitivity and specificity of BIS for predicting deep sedation based on clinical sedation scores. A cut-off BIS value for detecting deep sedation in children with CP was also calculated. A p value of 0.05 was considered to be statistically significant.

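### The planned Spearman coefficient, read naturally, pools minute-by-minute readings across children, so it cannot show how well BIS follows sedation within a child; a within-child coefficient should be reported beside it

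*Combined protocol and SAP*

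**What the plan says.** In the Study Protocol, two observers score UMSS and MOAAS "every minute during induction and maintenance of sedation". A third investigator records BIS "immediately before each assessment of clinical sedation score". Each child therefore supplies many BIS-score pairs; the number per child is not given.

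In the Statistical analysis plan, the sample-size paragraph states: "A minimum 19 participants was required to detect a correlation coefficient of 0.6 for repeated measures". It sets α at 0.05 and describes "a power of 80% to determine the validity of BIS values to detect deep sedation in children with cerebral palsy". It then adds: "We enrolled 22 patients, taking into consideration of 15% drop-out rate".

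The analysis paragraph says "BIS values were categorized into ranges of <50, 50-59, 60-69, 70-79, 80-89 and 90 or higher", and gives the correlation analysis in one sentence: "The correlation between the paired BIS value categories and clinical sedation scores was determined by Spearman rank correlation test". Neither section mentions a child effect, a within-child coefficient, a per-child summary, the use of one pair per child, or an adjustment for repeated readings.

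**The concern.** An ordinary Spearman coefficient has no place for the child. Applied to minute-by-minute pairs, it mixes two questions: does BIS move with the score as one child's sedation deepens, and do children with lower BIS on average also have deeper scores on average?

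The two answers can differ. If children have different BIS levels at the same depth of sedation, BIS may follow each child closely and the pooled coefficient still be modest. If children with low BIS are also the less responsive ones, the pooled coefficient may be sizeable although BIS hardly follows anyone. A reader who takes it as evidence of tracking, or who is led by the sample-size wording to think it a repeated-measures correlation, would misread it.

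This concerns what the point estimate measures, so a cluster-corrected p value or interval on the pooled coefficient does not settle it. Separately, the ordinary Spearman test treats every reading as independent.

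**Working it through.** **1. The plan's own figure.** Inputs from the sample-size paragraph: α 0.05 (sidedness not stated; two-sided assumed), power 80%, correlation 0.6. The Fisher-z formula is n = ((z₀.₉₇₅ + z₀.₈₀)/atanh(0.6))² + 3 = ((1.960 + 0.842)/0.693)² + 3 = 19.34. One-sided, it gives 15.87. Simulated power of the two-sided t-test for r is 78.8% at n = 18 and 81.3% at n = 19, so 19 is the minimum on that test. For drop-out, 19 × 1.15 = 21.85, giving 22; dividing instead, 19/0.85 = 22.35, giving 23. The stated 19 is thus reproduced by an ordinary correlation with one independent pair per child, with no number of readings needed.

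**2. What a within-child 0.6 would need.** With k readings in each of N children, the error degrees of freedom are N(k − 1) − 1. The same Fisher-z requirement gives N ≥ (16.34 + 2)/(k − 1): 19 children at k = 2, 10 at k = 3, 5 at k = 5 and 3 at k = 10. The agreement at k = 2 does not fit a plan that scores every minute.

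**3. What the pooled coefficient contains.** Spearman is a Pearson correlation on ranks, so this holds exactly:

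pooled r = √(hx·hy) × r_between + √((1 − hx)(1 − hy)) × r_within

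Here hx and hy are the between-child shares of the rank variance in BIS and in the score. The shares are not in the documents. In absolute values, a pooled 0.60 gives:

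- shares 0.4 and 0.2, r_between 0: r_within = 0.60/√(0.6 × 0.8) = 0.60/0.693 = 0.87;
- shares 0.4 and 0.4, r_between 0.9: r_within = (0.60 − 0.4 × 0.9)/0.6 = 0.24/0.6 = 0.40.

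**4. Simulation under assumptions.** 22 children with 10, 20 or 30 readings each, five sedation levels, the plan's six BIS ranges, 600 runs per setting. The intraclass correlations (ICC) and latent correlations are assumed. Signs are for UMSS, where a higher score is deeper. Ranges run over the numbers of readings.

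| Latent within / between correlation | ICC, both variables | Pooled Spearman | Within-child rank coefficient |
|---|---|---|---|
| −0.6 / none | 0 | −0.55 to −0.56 | −0.55 to −0.56 |
| −0.6 / 0 | 0.3 | −0.39 to −0.40 | −0.53 |
| −0.6 / 0 | 0.5 | −0.28 to −0.29 | −0.50 to −0.51 |
| −0.6 / +0.6 | 0.5 | −0.02 | −0.50 to −0.51 |
| 0 / −0.6 | 0.3 | −0.15 to −0.16 | 0.00 |
| 0 / −0.6 | 0.5 | −0.26 to −0.27 | 0.00 |

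In these settings the two coefficients coincide only in the first row, where children do not differ.

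**5. The ordinary p value.** With no association at either level, the ordinary Spearman p fell below 0.05 in 13% to 26% of runs at ICC 0.3 and 27% to 48% at ICC 0.5, against a nominal 5%.

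**The case against.** **Pooling is inferred.** The plan never says that readings are pooled. That is correct, but an ordinary Spearman test on pairs taken every minute, with no child term, is pooled by default. If something else is meant, the plan needs to say so.

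**The 0.6 is not defined as a within-child correlation.** This stands. A reader might infer that the trial was sized on within-child tracking and that the analysis departs from its own target. Only the label on the 0.6 points that way; the 19 follows from an ordinary correlation. Relabelling the 0.6 would add an error. Nor does the rank coefficient map directly onto 0.6: with a latent within-child correlation of −0.6 it was about −0.50 to −0.56.

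**Pooling has a use here.** This also stands, and it is the strongest objection. The plan seeks one BIS cut-off for children with cerebral palsy. If children differ in BIS at the same depth of sedation, a common cut-off works less well, and a validity coefficient ought to show that. One simulation assumed BIS means of 93, 84, 72, 60 and 50 at UMSS 0 to 4, within-child SD 8, and 8 induction plus 30 maintenance readings per child. As the between-child BIS SD rose from 0 to 15, the area under the ROC curve for UMSS 3–4 fell from 0.95 to 0.82 and the pooled coefficient weakened from −0.84 to −0.61. The within-child coefficient moved only from −0.81 to −0.77. Replacing the pooled coefficient would hide that loss, so the documents do not support dropping it.

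**Large distortions need large differences between children.** Fair. With the same BIS means and within-child SD, another simulation with a between-child SD of 5 moved the pooled coefficient only from −0.80 to −0.76. Strong mimicry needed a close link between a child's BIS offset and responsiveness.

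**Conclusion.** The point holds as a gap in what the plan can show. The planned coefficient, on its natural reading, blends within-child and between-child association. It cannot establish how well BIS follows sedation within a child, and it is not a repeated-measures correlation. Its ordinary p value also ignores the repeated readings.

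The decomposition is exact; the variance shares, ICCs and readings per child put into it are assumptions. A pooled 0.60 is compatible with a within-child 0.87 or 0.40, and the documents cannot say which is nearer.

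Two further inferences are not supported. One is that the coefficient in this trial is biased in a known direction: no variance components are given. The other is that 22 children are too few: a within-child 0.6 with many readings would need fewer children, not more.

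**What to change.** In the correlation part of the Statistical analysis plan:

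- State that the Spearman coefficient is computed over all accepted pairs from all children, if that is intended, and keep it.
- For UMSS and for MOAAS, add a within-child rank correlation: rank BIS and score, then correlate the ranks with child as a factor (a partial Spearman, or a linear model on ranks with child as a fixed factor; SPSS can fit either).
- Give intervals for both coefficients by resampling whole children, in place of the ordinary Spearman p value.
- State the reading in advance: the pooled coefficient bears on a common cut-off, the within-child coefficient on tracking.

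In the sample-size paragraph, state that the 19 corresponds to an ordinary correlation of 0.6 with one independent pair per child, and do not attach the 0.6 to the within-child coefficient.

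The cost is wording and a few lines of code; the data are already recorded by child. The downside is small: a child whose score never changes adds nothing to the within-child coefficient, so the number of such children should be reported.

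### The BIS cut-off, sensitivity and specificity appear to come from pooled repeated readings in 22 children, with no interval, clustering allowance or selection rule stated

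*Combined protocol and SAP*

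**What the plan says.** The Study Protocol section has sedation scored by two observers "every minute during induction and maintenance of sedation", with a third investigator recording BIS just before each score. The only inclusion filter, a signal quality threshold, applies to individual readings. The reference state is given as: "Deep sedation was defined based on clinical sedation scale categories: a UMSS score of 3-4 or a MOAAS score of 0-1".

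The Statistical analysis plan covers diagnostic accuracy in two sentences: "Receiver operating characteristic (ROC) curve analysis was performed to determine the sensitivity and specificity of BIS for predicting deep sedation", and then "A cut-off BIS value for detecting deep sedation in children with CP was also calculated". Neither sentence names an interval, a within-child method, a selection rule or any form of internal validation.

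Repetition is mentioned only in the sample-size paragraph: "A minimum 19 participants was required to detect a correlation coefficient of 0.6 for repeated measures". It is followed by: "We enrolled 22 patients, taking into consideration of 15% drop-out rate".

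**The concern.** Scoring each minute gives many BIS/score pairs per child, and pairs from one child resemble each other. The plan describes no per-child summary, so the natural reading is that all accepted readings were pooled. Two sources of uncertainty then go unreported. Twenty-two children carry less information than the number of readings suggests, and a cut-off picked as best in these data would come out differently in another sample.

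The stated aim is the validity of BIS for detecting deep sedation, and the cut-off is what turns a BIS value into a yes or no. A reader given one number cannot see how loosely it is determined. An interval that treats readings as independent would look more precise than it is.

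A smaller, separate gap is that the definition of deep sedation does not say whether the two scales are combined or analysed separately, nor whose score counts when the observers differ.

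**Working it through.** **Step 1. The plan's own figure.** Inputs from the Statistical analysis plan: correlation 0.6, α 0.05 (taken as two-sided), power 80%. Fisher z gives n = ((1.960 + 0.842)/atanh 0.6)² + 3 = (2.802/0.693)² + 3 = 19.34. Simulated power of the two-sided test is 81.4% at n = 19 and 78.8% at n = 18, so 19 is reproduced. Then 19 × 1.15 = 21.85, or 22 children. This is an ordinary calculation for a correlation. It says nothing about the precision of sensitivity, specificity or a cut-off.

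**Step 2. Hand check of clustering at a fixed cut-off.** Assumed: sensitivity 0.80 and 10 deep readings per child, so 220 readings. The naive half-width is 1.96 × √(0.8 × 0.2/220) = 5.3 points. The design effect is DE = 1 + (10 − 1) × ICC, and naive coverage is 2Φ(1.96/√DE) − 1.

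| ICC | DE | Half-width allowing for clustering | Naive coverage |
|---|---|---|---|
| 0.1 | 1.9 | ±7.3 points | 85% |
| 0.3 | 3.7 | ±10.2 points | 69% |
| 0.5 | 5.5 | ±12.4 points | 60% |

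The ICC here belongs to the yes/no classification. In the next steps it belongs to BIS itself, so the two sets of figures should agree in direction and scale but not exactly.

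**Step 3. Simulation model (all inputs assumed except the 22 children).** Each child has 20 readings, and half of all readings are deep on average, with the share varying between children. BIS is normal within each state with a child random intercept (ICC 0.3) and is rounded to integers. The non-deep mean is 75. With AUC 0.83 the deep mean is 75 − SD × √2 × 0.954, which is 64.2 at SD 8 and 58.8 at SD 12. A reading is called deep if BIS is at or below the cut-off, and the cut-off maximises the Youden index.

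The 95% range of the chosen cut-off over repeat studies is about 65 to 73 at SD 8 and 61 to 72 at SD 12. The middle half is 68 to 70 and 65 to 68, so it spans only 2 to 3 points.

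**Step 4. What that range means for accuracy.** For cut-off c, true sensitivity is Φ((c + 0.5 − deep mean)/SD) and true specificity is 1 − Φ((c + 0.5 − 75)/SD). The Youden column uses the rounded values.

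| SD | Cut-off | Sensitivity | Specificity | Youden |
|---|---|---|---|---|
| 8 | 65 | 0.56 | 0.88 | 0.44 |
| 8 | 73 | 0.88 | 0.57 | 0.45 |
| 12 | 61 | 0.59 | 0.87 | 0.46 |
| 12 | 72 | 0.87 | 0.58 | 0.45 |

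The maximum possible Youden index is 0.50, and its mean true value at the chosen cut-off is 0.489.

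**Step 5. Sources of spread.** Width of the 95% range of apparent sensitivity:

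| Setting | Independent readings, fixed cut-off | Clustering only | Re-selection only (ICC 0) | Both |
|---|---|---|---|---|
| AUC 0.83, ICC 0.3 | 0.11 | 0.19–0.20 | 0.24–0.25 | 0.25–0.26 |
| AUC 0.93, ICC 0.3 | 0.09 | 0.15 | 0.15–0.16 | 0.16–0.17 |
| AUC 0.93, ICC 0.5 | – | 0.18–0.19 | 0.15–0.16 | 0.19 |

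The two effects overlap. Re-selection is larger in the first row, they are about equal in the second, and clustering is larger in the third.

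**Step 6. Coverage of true sensitivity at the chosen cut-off, nominal 95% (main case).**

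| Interval | Coverage |
|---|---|
| Reading-level Wilson | 72–76% |
| Whole-child bootstrap, cut-off fixed | 87–91% |
| Reading-level bootstrap, cut-off re-selected | 90–91% |
| Whole-child bootstrap, cut-off re-selected | 93% |

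Reading-level Wilson coverage is about 95% at ICC 0 and about 66–67% at ICC 0.5, so its shortfall comes from clustering. For AUC, where no cut-off is chosen, coverage is 79–80% with reading-level and 88–90% with whole-child resampling. Over 26 settings the whole-child bootstrap with re-selection was closer to 95% than Wilson in 25.

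**Step 7. Optimism.** Choosing and evaluating the cut-off on the same data overstates sensitivity and specificity by about 1.5 points each in the main case, or about 3 points on the Youden index.

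**The case against.** The strongest reply is that the plan is simply short. It names no interval for any estimate, so silence here does not show that none was calculated. A reader might infer that the cut-off was reported bare; the documents support only that no interval is stated. Pooling is likewise inferred from the pairing each minute and the reading-level filter, and is not stated. This stands, and it limits the point to what the plan should say. It does not remove it: the reader still needs to know how any intervals were made, because default reading-level ones would mislead.

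Second, quoting the swing in sensitivity alone (0.56 to 0.88) invites the inference that BIS might discriminate far worse than reported. That is not so. Specificity moves the other way, and even an extreme cut-off costs only about 4 to 6 points of Youden index (0.50 against 0.44 to 0.46).

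Third, clustering adds little to the spread of the cut-off itself: at SD 8 the range is 66 to 72 at ICC 0 and about 65 to 73 at ICC 0.3. Whole-child resampling also gains only 2 to 3 coverage points for sensitivity over reading-level resampling with re-selection, and at ICC 0.1 the two perform alike. This stands. The case for resampling children rests mainly on AUC and on ordinary reading-level intervals.

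Fourth, the cut-off range is about as wide as one of the plan's 10-point BIS bands ("BIS values were categorized into ranges of <50, 50-59, 60-69, 70-79, 80-89 and 90 or higher"). The plan ties those bands to kappa and rank correlation and does not say whether the ROC analysis used raw or banded BIS, so the comparison gives scale only.

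Finally, the plan gives the cut-off a modest place, since the study was sized on a correlation. That is fair, and it fits describing the cut-off as exploratory.

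**Conclusion.** The point holds as a cheap improvement. The plan derives sensitivity, specificity and a cut-off from what appear to be pooled readings in 22 children. It states no interval, no allowance for clustering, no selection rule and no allowance for same-data selection.

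Under the assumed inputs, the cut-off is uncertain by 8 points (SD 8) to 11 points (SD 12), and an ordinary interval for sensitivity covers about three quarters of the time instead of 95%. The documents give none of readings per child, ICC, SD, AUC, share of deep readings or selection rule, so these figures show scale only. Given positive within-child correlation, the direction does not depend on them. Even with one reading per child, the unstated interval and the same-data cut-off would remain.

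Two stronger readings are not supported. A reader might infer that one effect always dominates, but which is larger depends on AUC and ICC. A reader might also infer that same-data selection makes the accuracy figures badly optimistic, but about 1.5 points per measure is minor.

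**What to change.** Report AUC, sensitivity, specificity and the cut-off with approximate 95% intervals from a bootstrap that resamples whole children and repeats the cut-off selection in every resample. State the selection rule (for example, maximum Youden index), whether raw or banded BIS was used, whether the two scales are combined or separate, and whose score counts when the observers differ. Always give sensitivity and specificity together. Describe the cut-off as exploratory. Because the plan describes enrolment and analysis as already done, label the intervals a post hoc reanalysis. Optimism-corrected values from the same bootstrap are optional.

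The cost is a short script on existing data and a few lines of text. Intervals become wider. With 22 children they are themselves only approximate: coverage for sensitivity was 84–97% in the settings checked, and the text should say so.
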